4 STUDY DESIGN

4.1 Treatment Design

This will be a multicenter, open trial of oral letrozole versus combination of oral letrozole and clomiphene citrate for the treatment of infertility in patients with oligo-ovulation or anovulation. Patients will be randomized to one of two treatment arms, to receive either an initial dose of letrozole 2.5 mg alone or clomiphene citrate 50 mg and letrozole 2.5 mg for 5 days during their menstrual cycle. Letrozole dosing will be escalated in a stair-step fashion based on ovulation results. Max dose of letrozole will not exceed 7.5 mg.

Participation in active treatment will last for up to 3 treatment cycles, approximately up to 15 weeks. Participants will be monitored at monthly intervals during expected mid-luteal phase to evaluate response to medication by evaluating ultrasound and progesterone parameters.

The dose will be adjusted according to response at mid-luteal visit.

- Anovulatory progesterone level < 3 and no evidence of follicular development and corpora lutea → increase letrozole dose on that day. This would be considered start of new treatment cycle (CD3).
- Anovulatory progesterone level < 3 with evidence of follicular development (follicle ≥14 mm) → repeat progesterone level based on LH testing (6-8 days following positive) or at 2 weeks if no positive → increase dose at menses visit (2nd progesterone is ovulatory) or increase dose at time of second progesterone if level < 3.

- Progesterone level ≥3 → maintain same dose for next treatment cycle

Anytime ovulation induction medication is started, pregnancy test to be performed prior to initiation of new treatment cycle.

Randomization will be stratified by site, age (< 35 versus \geq 35) and BMI (< 30 and \geq 30) to ensure similar comparison groups in these characteristics that highly impact outcomes. Randomization will be via a computer based central randomization to ensure adequate allocation concealment.

Enrollment will take approximately 20 months if ~ 10 subjects are enrolled per month. Active subject participation will be through completion of 3 cycles. We will follow up with patient regarding pregnancy and delivery outcomes.

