7.3 Intermediate Visits

Participants will return for a midluteal study visit on cycle day 21-24 or 7-9 days following positive ovulation prediction test to determine if ovulation occurred. This visit will include an ultrasound and a progesterone lab.

If there is no ovulation, the daily dose of letrozole will be increased by 2.5 mg, to begin immediately. During the first cycle after letrozole dose increase, participants would receive 5mg daily for 5 days. If participants receive a second letrozole dose increase, they would receive 7.5 mg Letrozole daily for 5 days. The maximum dose for Letrozole in this study is 7.5 mg. CC 50 mg will be given on the same days as the letrozole in all cycles in the combination arm. Midluteal visits will be performed in all cycles. Each participant will complete a maximum of 3 cycles of medical therapy. On average we expect this to be about 4 months time, however, delayed ovulation, a biochemical pregnancy, or 1st trimester pregnancy loss in the first or second treatment cycle could delay the start of subsequent cycles, and therefore would extend active participation.

Cycle 1 Midluteal Visit

Timing will be based on LH testing, ideally around 7-8 days post-positive test or CD21-24 if no positive test

- Transvaginal ultrasound to assess for corpora lutea and endometrial thickness and pattern
- Serum progesterone assessment for ovulation
- Review subject calendar log and record adverse events as reported by subject or observed by investigator.
- Determine dosage for next cycle based on ultrasound and progesterone results and record in RedCap
 - If there is no ovulation, the daily dose of letrozole will be increased by 2.5 mg (5mg). The combination arm will continue to receive CC 50mg along with the increased letrozole dose.
 - If there is ovulation, treatment will be repeated in the next cycle with the same dose of letrozole. The combination arm will continue to receive CC 50mg along with letrozole 2.5mg.
- Schedule a follow up Progesterone lab if necessary
 - Participants with anovulatory progesterone levels (<3 ng/ml) and evidence of follicular development will return for a repeat progesterone level assessment in 10-14 days.
 - Participants with elevated anovulatory progesterone levels (1.5 < P4 < 3.0) and corpus luteum on ultrasound will return for a repeat progesterone level assessment in 2-3 days

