- Dispense pregnancy test and medication for next cycle and review instructions for medication (dispense medication if unable to return to pick up meds, if can easily return, have participant return for med pick up)
 - Participants without ovulation nor evidence of follicular development are to complete pregnancy test and begin medication at new dose immediately following negative pregnancy test
 - Participants with ovulation are to wait until onset of menses, or two weeks after midluteal visit to complete pregnancy test. They can begin medication at same dose following negative pregnancy test. Participants with a positive pregnancy test will be moved to pregnancy track and will return dispensed medication at their next study visit.

- Collect any unused medication from current cycle and document participant compliance in RedCap
- Record results of ultrasound and serum progesterone in RedCap

Cycle 1 Follow-up Midluteal Visit*

Participants with anovulatory progesterone levels (<3 ng/ml) and evidence of follicular development at their midluteal visit will return for a repeat progesterone level assessment in 10-14 days. This can be performed at a local lab if the participant prefers.

- Serum progesterone assessment for ovulation
- Review subject calendar log and record adverse events as reported by subject or observed by investigator.
- Review instructions for previously dispensed medication/dispense medication if not yet dispensed
 - Participants without ovulation are to complete pregnancy test and begin medication at new dose following either a spontaneous menses or withdraw bleed and a negative pregnancy test. They can begin taking medication to induce a withdraw bleed on cycle day 35, following a negative pregnancy test.
 - Participants with ovulation are to wait until onset of menses, or two weeks after midluteal visit to complete pregnancy test. They can begin medication at new dose following negative pregnancy test (if ovulation did not occur on or before cycle day 21). Participants with a positive pregnancy test will be moved to pregnancy track and will return dispensed medication at their next study visit.
 - Participants who were initially anovulatory at a study visit prior to cycle day 21, who are ovulatory at a follow up visit by cycle day 21 will be maintained on the same dose of medication. This may occur if participant's study visit was moved up due to an early false positive ovulation prediction test.

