- Record results of serum progesterone in RedCap

Cycle 1 Menses Check-In/Cycle 2 Start (menses from Cycle 1)*

Two weeks post Midleuteal visit if no menses before then

Participants with ovulation are to wait until onset of menses, or two weeks after midluteal visit to complete pregnancy test. They can begin medication at new dose following negative pregnancy test. This visit can be completed remotely with participant logging information in RedCap. If they don't have medication, they will come in to pick it up. Participants with a positive pregnancy test will be moved to pregnancy track and will return dispensed medication at their next study visit.

Cycle 2 Midluteal Visit

Timing will be based on LH testing, ideally around 7-8 days post-positive test or CD21-24 if no positive test.

- Transvaginal ultrasound to assess for corpora lutea and endometrial thickness and pattern
- Serum progesterone assessment for ovulation
- Review subject calendar log and record adverse events as reported by subject or observed by investigator.
- Determine dosage for next cycle based on ultrasound and progesterone results and record in RedCap
 - If there is no ovulation, the daily dose of letrozole will be increased by 2.5 mg.
 - Participants on Letrozole 2.5 this cycle will be increased to Letrozole 5.0 in cycle 3.
 - Participants on Letrozole 5.0 this cycle will be increased to Letrozole
 7.5 in cycle 3.
 - The combination arm will continue to receive CC 50mg along with the increased letrozole dose.
 - If there is ovulation, treatment will be repeated in the next cycle with the same dose of letrozole. The combination arm will continue to receive CC 50mg along with either Letrozole 2.5 or 5.0.
- Schedule a follow up progesterone lab if necessary
 - Participants with anovulatory progesterone levels (<3 ng/ml) and evidence of follicular development will return for a repeat progesterone level assessment in 10-14 days (lab can be done locally or at clinic site).

- Participants with elevated anovulatory progesterone levels (1.5 < P4 < 3.0) and corpus luteum on ultrasound will return for a repeat progesterone level assessment in 2-3 days
- Dispense pregnancy test and medication for next cycle and review instructions for medication
 - Participants without ovulation nor evidence of follicular development are to complete pregnancy test and begin medication at new dose immediately following negative pregnancy test

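### The Cycle 1 and Cycle 2 menses check-in paragraphs in 7.3 start every participant with ovulation at a new dose, although the rest of the protocol keeps on-time ovulators on the same dose

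*Combined protocol and SAP*

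**What the plan says.** Section 4.1 sets the dose rule. When the midluteal progesterone is 3 ng/mL or more, the instruction is to "maintain same dose for next treatment cycle". When the first level is below 3 with a follicle of at least 14 mm, progesterone is repeated, and even if the second level is ovulatory the plan is to "increase dose at menses visit (2nd progesterone is ovulatory").

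Section 7.3 repeats the rule for on-time ovulators at the Cycle 1 and Cycle 2 midluteal visits: "If there is ovulation, treatment will be repeated in the next cycle with the same dose of letrozole", and in the medication instructions, "They can begin medication at same dose following negative pregnancy test". The dose is set at that visit: "Determine dosage for next cycle based on ultrasound and progesterone results and record in RedCap".

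The follow-up midluteal visits in 7.3 allow ovulators a new dose only if ovulation did not occur by cycle day 21. Women first tested before day 21 "who are ovulatory at a follow up visit by cycle day 21 will be maintained on the same dose of medication".

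The Cycle 1 and Cycle 2 menses check-in paragraphs, also in 7.3, then say of participants with ovulation: "They can begin medication at new dose following negative pregnancy test. This visit can be completed remotely". Neither paragraph mentions the timing of ovulation.

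**The concern.** The check-in sentence closely follows the midluteal instruction, except that *same* has become *new* and the day-21 condition of the follow-up visits is missing. It therefore gives on-time responders the opposite instruction to the one they received at the midluteal visit.

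Tablets can change hands at this step. Section 4.2 prefers that participants return on cycle day 1-3 for medication, the Cycle 1 midluteal text encourages return for pick-up, the Cycle 1 check-in paragraph has women without medication come in for it, and Appendix A marks dispensing in the menses check-in column. Staff working from the check-in paragraph could give a responder a higher dose than the design intends.

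At stake is what happens in cycles 2 and 3: side effects, number of corpora lutea, endometrial thickness and multiple gestation. Section 3.2 plans to examine endometrial thickness and corpora lutea by dose, which presumes that one dose rule was followed. Section 2.2.1 states that the multiple-pregnancy rate of the combination is not known.

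**Working it through.** The plan gives no figure to reproduce here. The check is a side-by-side reading of the dose instructions, followed by the size of one literal error.

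**Next-cycle dose by place in the protocol**

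| Place | Group addressed | Next dose |
|---|---|---|
| 4.1 | Midluteal progesterone at least 3 | Same |
| 4.1 | First level below 3, follicle present, second level ovulatory | Increased |
| 4.1.1 | Escalation is for those who do not ovulate | Same for ovulators (implied) |
| 6.1.1 | Increase for no ovulation or significantly delayed ovulation | Same for on-time ovulators (implied) |
| 7.3, midluteal visits, Cycles 1 and 2 | Ovulation | Same |
| 7.3, follow-up midluteal visits, Cycles 1 and 2 | Ovulation on the repeat test | New, unless ovulation was by day 21 |
| 7.3, menses check-in, Cycles 1 and 2 | Ovulation, no condition | New |

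The last row is the only one that sends an on-time ovulator to a new dose.

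**Does *new dose* simply mean the dose for the next cycle?** The midluteal lists in 7.3 use *same dose* for ovulators and *new dose* for women without ovulation or follicular development, so the two terms are opposites there.

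**Does the check-in cover on-time ovulators?** Section 4.2 has each participant check in at menses, so it does.

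**Size of one literal error**, assuming that *new dose* means the next letrozole step of 2.5 mg:
- Cycle 2 start: 2.5 + 2.5 = 5.0 mg instead of 2.5 mg.
- Cycle 3 start, from 5.0 mg: 5.0 + 2.5 = 7.5 mg instead of 5.0 mg.
- Both check-ins followed literally, from 2.5 mg: 2.5 + 2 × 2.5 = 7.5 mg, which equals the stated maximum.

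With at most three cycles there are only two check-ins at which this can happen, so the error cannot pass 7.5 mg.

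**Effect on the primary outcome.** The misdirected text applies only to women who have already ovulated. Under the cumulative outcome in 12.2 an on-time ovulator already counts as a success, and a wrong dose afterwards does not change that. Analyses that use the later cycles would include the escalated cycles.

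**The case against.** The strongest case on the other side is that the check-in paragraph is not where the dose is set. The dose is determined and recorded in REDCap at the midluteal visit. Section 6.1.1 has tablets packaged and labelled by dose, section 6.2 requires the tablet number to be verified before dispensing, and section 11 plans REDCap flags for deviations in dosing, followed by contact with the site. An error would need staff to set aside a recorded dose because of two words. All of this stands. It is why the point is minor and why a separate retrospective search for escalated responders is not needed.

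The asterisk is the second argument. The check-in headings in 7.3 carry the same mark as the follow-up midluteal headings, and Appendix A defines it as a progesterone below 3 with follicular development. On that reading the paragraphs were meant only for delayed ovulators, for whom section 4.1 does raise the dose at the menses visit. This may explain how the wording arose, but it does not cure it: 7.3 does not define the mark, Appendix A does not place it on the check-in column, 4.2 applies the check-in to each participant, and the day-21 condition would still be missing.

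Third, the follow-up visit lists end with "Record results of serum progesterone in RedCap" and name no step for recording a dose. This matters little. A first level below 3 already leads to an increase at the midluteal visit, and only the day-21 exception would reverse it.

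A reader might also infer that many responders would be overdosed, by applying the cycle-1 ovulation rates (43% and 77% in the pilot, 49.4% on letrozole in PPCOS II) to 92 women per arm. The documents do not support that. Those are point estimates of ovulation from other studies. They do not separate on-time from delayed ovulation, and they say nothing about who collects tablets at cycle start or who would be given the wrong number.

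**Conclusion.** The two check-in paragraphs are wrong as written. They contradict the dose rule stated or implied everywhere else for on-time ovulators, and they drop the day-21 condition for delayed ones. The error is minor: the intended rule is recoverable, several controls stand between the text and a dose taken, and one literal error is a single 2.5 mg step within the 7.5 mg maximum.

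The conclusion rests on reading *new dose* as an increased dose, as 7.3 uses it elsewhere, and on the check-in applying to all participants, as 4.2 says. The number of women affected cannot be estimated from the documents, and nothing in them shows that any responder has been escalated.

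Two stronger readings should be set aside. The point does not threaten the primary comparison of cumulative ovulation, the sample size or the test. Nor is the day-21 exception a fault in itself: 7.3 explains it as covering a visit moved up by an early false-positive ovulation test.

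**What to change.** In both menses check-in paragraphs of 7.3, replace *new dose* with wording to this effect: the dose determined at the midluteal or follow-up midluteal visit (same dose if the first progesterone was at least 3 ng/mL or ovulation occurred on or before cycle day 21; increased dose if ovulation was shown only on the repeat progesterone and occurred after cycle day 21).

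Optionally, add one line to the Cycle 1 and Cycle 2 follow-up midluteal visit lists to update the dose in REDCap when the day-21 exception applies.

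The cost is a wording amendment to two paragraphs and, if taken up, one line in each of two lists. Sections 4.1 and 4.2 need no change for this point, and there are no extra visits, patients or analyses.

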7.4 Pregnancy Track Visits (part of routine care obstetrical care)

Patients who report a positive urine pregnancy test will have a serum hCG to confirm pregnancy, with a follow up serum hCG 48-72 hours after initial hCG. Results from patients' viability ultrasound will be obtained through chart abstraction. Patients with ongoing pregnancies will be followed through postpartum with 3 remote visits. Patients who experience biochemical pregnancy or 1st trimester pregnancy loss in pregnancies resulting from their 1st or 2nd treatment cycle may return to the treatment track and begin their next treatment cycle after one normal menses and a negative pregnancy test.

Pregnancy Lab Visit

Participants with positive urine pregnancy test will have pregnancy confirmed with serum hCG assessment. This can be performed at a local lab if the participant prefers.

- Serum hCG assessment for pregnancy
- Review subject calendar log and record adverse events as reported by subject or observed by investigator.
- Review instructions for pregnancy follow up, return to treatment track, or end of study as necessary
- Review plans for pregnancy care and obtain consent for obtaining information if pregnancy provider records will need to be requested and consent to obtain medical information on file is not up to date
- Collect any unused medication from current or previous cycle(s) and document participant compliance in RedCap
- Record results in RedCap

Pregnancy Lab Visit 2

Pregnant participants will have a repeat serum hCG assessment 48-72 hours after initial hCG. This can be performed at a local lab if the participant prefers.

- Serum hCG assessment
- Review instructions for pregnancy follow up, return to treatment track, or end of study as necessary
- Review plans for pregnancy care and obtain consent for obtaining information if pregnancy provider records will need to be requested and consent to obtain medical information on file is not up to date
- Record results in RedCap

Ongoing Pregnancy Follow up

Approximately 3 weeks after positive pregnancy test.

- Obtain viability ultrasound and enter results in RedCap
- Review instructions for pregnancy follow up, return to treatment track, or end of study as necessary
- Review plans for pregnancy care and obtain consent for obtaining information if pregnancy provider records will need to be requested and consent to obtain medical information on file is not up to date

12-15 Week Pregnancy Follow up

Review records (if available) to determine if participant has experienced a loss.

- Participant will complete 12-15 week pregnancy follow up questionnaire via online surveys or phone.
- Review instructions for pregnancy follow up, return to treatment track, or end of study as necessary
- Review plans for pregnancy care and obtain consent for obtaining information if pregnancy provider records will need to be requested and consent to obtain medical information on file is not up to date
- Record abstraction details or participant responses in RedCap

Postpartum Pregnancy Follow up

- Review records (if available) to determine outcome of pregnancy.
- Participant will complete postpartum pregnancy follow up questionnaire via online surveys or phone.
- Review instructions for return to treatment track or end of study as necessary
- Review pregnancy care received and delivery and obtain consent(s) for obtaining information for mother if pregnancy provider records will need to be requested and consent to obtain medical information on file does not include named providers
- Obtain consent(s) for obtaining information for infant(s) if delivery records will need to be requested
- Record infant date of birth, birth weight and length, and any birth defects noted by the pediatrician or mother in RedCap. This information can be obtained from mother the RedCap Postpartum survey.
- Have participant complete questionnaires (GAD7, PHQ9, FertiQoL, and Perceived Stress Scale, or if participant prefers to complete online, provide instructions on completing forms after visit

7.5 Final Study Visit/Cycle 3 Menses check in

An end of treatment visit or phone call will occur after menses occurs with a negative pregnancy test or negative pregnancy test in the case of an anovulatory treatment cycle or following a positive pregnancy test. This visit will be held within 1 week of outcome (negative or positive pregnancy test) Any unused study medication will be returned to the

study team at this visit. Participants who completed paper journal logs will submit any remaining journal logs at this visit, and the end of treatment questionnaire will be completed.

Final Study Visit

- Record adverse events as reported by subject or observed by investigator.
- Record results of home urine pregnancy test and subsequent serum hCG tests.
- Review subject calendar log and record adverse events as reported by subject or observed by investigator.
- Collect any unused study medication and document participant compliance in RedCap
- Complete end of treatment questionnaire with subjects if they have not completed online
- Complete post questionnaires (PHQ9, GAD7, and Perceived Stress Scale) with participant if they have not completed online
- Provide final instructions to subject

7.6 Missed Study visits

In the event a subject is unable to complete their midluteal ultrasound, progesterone lab, or follow up progesterone lab, ovulation will be assessed by presence and timing of spontaneous menses.

Subjects can postpone a cycle if they know that they will not be able to complete midluteal visit components within the projected window, taking a cycle off between study cycles. Timing of cycles will be captured in RedCap. However, in the event of unexpected inability to attend, as may occur if a subject were to contract a COVID-19 infection during their study cycle, menses can be used as an indication of ovulation in place of progesterone lab and ultrasound results.

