3.1.1 Primary Outcome Measure

The primary outcome measure is the occurrence of ovulation during the study period. Ovulation is defined as a mid-luteal progesterone level > 3 ng/mL. This will be tested 6-8 days following the patient reporting of an LH surge. If no LH surge is detected the lab will be drawn on cycle day 21-24. We will also analyze the ovulation rate of the follow up progesterone level.

We will utilize an intent-to-treat approach for the primary analysis of ovulation rate (utilizing the first progesterone level of each cycle) within the two treatment arms. If it is determined that timing of the initial progesterone level is inaccurate based on LH testing or patient symptoms, the progesterone test that is most clinically in line with accurate timing (6-8 days post LH surge) will be used. Ovulation rate will also be reported in those with a delayed response to treatment (needed repeat progesterone level due to anovulatory mid-luteal P4 level and follicle ≥ 14 mm). Patients will be analyzed according to the treatment group to which they are assigned, even if they did not receive the intended treatment or received only a portion of it. We will also perform a per protocol analysis to include only those patients who initiate treatment. Thus, those that are randomized but do not take the treatment due ineligibility will be excluded from the per protocol analysis. This per protocol analysis will provide data that is helpful to clinicians as it will include only those who initiated treatment.

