5 STUDY ENROLLMENT AND WITHDRAWAL

5.1 Study Population

184 women with WHO class II anovulation/PCOS actively seeking pregnancy (or 92 per each treatment arm) aged \geq 18 to \leq 40 years will be randomized. The overall goal of enrollment criteria is to identify a population of healthy women with anovulatory or oligo-ovulation (WHO Class II anovulation) and infertility not specified by another cause. Infertility will be determined by clinical history. PCOS will be determined by including two of three findings: oligo- or anovulation, hyperandrogenism or polycystic ovaries on ultrasound. Definitions are from the 2018 Recommendations from the international evidence-based guideline for the assessment and management of polycystic ovary management(3).

- Oligo-ovulation: cycles less than 21 days or greater than 35 days or less than 8 cycles per year
 - Ovulatory dysfunction/Anovulation: women with regular cycles with anovulatory progesterone or with amenorrhea
- Polycystic ovarian morphology (PCOM) on ultrasonography: follicle number (measuring 2-9 mm) per ovary of ≥ 20 and/or ovarian volume >10 ml on either ovary, ensuring no corpora lutea, cysts or dominant follicles are present if using volume only.
- Hyperandrogenism: determined by evidence of clinical or biochemical hyperandrogenism
 - o Clinical: symptoms and signs of hirsutism, acne or alopecia
 - Biochemical: elevations in calculated free testosterone or free androgen index (Total Testosterone level divided by SHBG level and multiply by 100). Levels should not have been assessed while on combined hormonal contraceptive
- If PCOS criteria is not met, normogonadotropic anovulation should be met with confirmation of anovulation/olig-ovulation and normal FSH and estradiol levels.
- Infertility: Inability of couple to achieve successful pregnancy after 12 months of regular timed unprotected intercourse in women less than 35 years of age; and after 6 months of regular intercourse without use of contraception in women 35 years and older(20). If in the clinical case of anovulation/oligo-ovulation, 12 month period of time "infertility" is not necessary.

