12.2 Statistical Analysis

All analyses will utilize the intention-to-treat (ITT) principle. All statistical tests of hypotheses will be two-sided. Baseline characteristics will be summarized by treatment arm. The primary outcome, cumulative ovulation, will be analyzed by comparing proportions utilizing a chi square test with significance set at 0.05. Dichotomous secondary outcomes will be analyzed in the same manner as the primary outcome. Two-sided t-tests will be used to compare endometrial lining thickness. Wilcoxon-Mann-Whitney tests will be used to compare number of corpora lutea. Time to pregnancy will be analyzed as a continuous variable using Kaplan-Meier survival analysis. Per-protocol analyses will be conducted to provide additional insight.

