12.4 Missing Data

Every attempt will be made to obtain the full set of outcome values for each participant. Despite this effort, we expect there will be some missing data due to dropouts and missed visits. Missing data for binary outcomes will be calculated with both conservative (assumed negative (e.g. no ovulation) and liberal with assumed yes ovulation unless later data contradicts this. If necessary, imputation will be used.

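### A missed-test cycle can be called ovulatory from menses with no cut-off, no missing-data rule is named as primary, and patient symptoms can displace the first progesterone

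*Combined protocol and SAP*

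**What the plan says.** **Definition.** Section 3.1.1 defines ovulation by a mid-luteal progesterone threshold alone. It ties the intent-to-treat approach to the "primary analysis of ovulation rate (utilizing the first progesterone level of each cycle"; delayed responses found on a repeat test are reported in addition. Section 12.2 adds: "The primary outcome, cumulative ovulation, will be analyzed by comparing proportions utilizing a chi square test".

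**Missed visits.** Section 7.6 covers a missed ultrasound, progesterone or follow-up progesterone: "progesterone lab, or follow up progesterone lab, ovulation will be assessed by presence and timing of spontaneous menses". Its last sentence, on unexpected absence, says only that "menses can be used as an indication of ovulation in place of progesterone lab and ultrasound results".

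**Bleeding without ovulation.** For the cycle 1 follow-up visit, section 7.3 says: "Participants without ovulation are to complete pregnancy test and begin medication at new dose following either a spontaneous menses or withdraw bleed". Section 5.1 describes ovulatory dysfunction as "women with regular cycles with anovulatory progesterone or with amenorrhea".

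**Missing data.** Section 12.4 handles missing binary outcomes both ways: "conservative (assumed negative (e.g. no ovulation) and liberal with assumed yes ovulation unless later data contradicts this". It then adds: "If necessary, imputation will be used".

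**Replacing the first value.** Section 3.1.1 lets another progesterone stand in for the first when timing is judged wrong from LH testing or patient symptoms. Section 4.1 says that patients know their treatment.

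**The concern.** Menses is not the defined endpoint, and the protocol itself allows for it without ovulation, so a menses-based call can wrongly label a cycle ovulatory. The endpoint is cumulative over up to three cycles. One false yes in any cycle therefore makes a woman a success, whereas one assumed no matters only if no other cycle is ovulatory.

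As worded, 7.6 is also triggered by a missed ultrasound or follow-up test. It could then be invoked even when a first progesterone is on file.

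No section says whether a menses-based call counts as observed or missing, whether 7.6 comes before 12.4, or which version of 12.4 enters the chi-square test. The choice could be made after open-label data have been seen. The symptom-based replacement adds a second discretionary step, with no decider named and no masking to arm or result.

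**Working it through.** **1. Inputs.** From the documents: two-sided chi-square at 0.05 (12.2); 80% power, 20 points absolute, 10% dropout and 92 per arm (12.1.4); up to three cycles. Assumed, because the documents do not state them: the control rate, the share of tests missed per cycle, and how missed cycles are called.

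**2. The plan's own figure.** With 60% v 80% and pooled variance, n = [1.96√(2×0.7×0.3) + 0.842√(0.6×0.4 + 0.8×0.2)]² / 0.2² = 81.2, so 82. Then 82/0.9 = 91.1, so 92 per arm, which matches. Without continuity correction, control rates of 58.2% to 60.7% reproduce 92. The sample size is not in dispute, and 60% v 80% is the main illustration. The table in 12.1.1 implies that at least 204/360 = 56.7% of letrozole women ovulated within three cycles in the cited trial, so 50% lies below that source and is shown only for range.

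**3. The sections side by side, for a cycle with no first progesterone.**

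| Section | Rule | Gap |
|---|---|---|
| 3.1.1 | progesterone | none available |
| 7.6 | menses | no window; timing dropped in the last sentence; silent on a woman who conceives and so has no menses |
| 12.4 | no, yes, or imputed | no primary version; menses not mentioned |
| 12.1.3, 12.2 | chi-square | does not say which version is used |

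**4. Effect on power (92 per arm, equal missingness, exact rejection probability).** Let p be the true cumulative rate, m the share of tests missed per cycle, and b the share of missed non-ovulatory cycles called ovulatory. Missed cycles that were truly ovulatory are taken as called ovulatory. The called-yes rate is 1 − (1 − p)(1 − mb)³, so the difference shrinks by (1 − mb)³. For m = 0.10 and b = 1 the factor is 0.9³ = 0.729. The rates become 1 − 0.4×0.729 = 70.8% and 1 − 0.2×0.729 = 85.4%, a difference of 14.6 points instead of 20.

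| Scenario | 50 v 70 | 60 v 80 | 70 v 90 |
|---|---|---|---|
| Nothing missing | 79% | 85% | 94% |
| 10% of tests per cycle, all called ovulatory | 59% | 67.5% | 82% |
| 5%, all called ovulatory (or 10%, b = 0.5) | 70% | 77% | 89% |
| 10% per cycle, all called not ovulated | 75–79% | 82–85% | 92–94% |
| 10% of women lost, assume-no (0.9p) | 68% | 72% | 79% |
| 10% of women lost, assume-yes (0.1 + 0.9p) | 73% | 80% | 90% |

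The ranges in the fourth row run from independent cycles to women who either always or never ovulate. Which rule costs more power depends on the loss pattern: assume-yes for missed single tests, assume-no for women lost before any observed ovulation.

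**5. Type I error.** With equal missingness it stays near 5%. With an assumed loss of 5% v 15% and the same true rate (50%, 60% or 70%) in both arms:

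- Whole-woman loss: 10–17% (assume-no), 8–10% (assume-yes).
- Per-cycle loss, assume-no: 8–11% if cycles are independent, but 4.6–5.1% (no inflation) if women always or never ovulate.
- Per-cycle loss, all called ovulatory: 22–41%. If only a quarter of the missed non-ovulatory cycles are called ovulatory: 6–7%.

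**6. A borderline result.** With 50/83 v 62/83 observed and 9 women per arm undetermined, p is 0.047 excluding them, 0.070 with all no and 0.052 with all yes. At about the planned effect (50/83 v 66/83) the three values are 0.007, 0.015 and 0.008, all significant.

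**The case against.** **The sections may fit together.** Section 7.6 could guide visits and 12.4 the analysis, and the later data mentioned in 12.4 could include menses logs. That is a fair reading, but no text states it, and 12.4 would still name no primary version. Its promise of both extremes is useful as sensitivity analysis.

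**Misses may be few, and timing may help.** Section 7.6 lets a participant postpone a cycle when she foresees a miss. Section 7.3 permits an induced bleed from cycle day 35, so timing might separate late anovulatory bleeds. Both points stand. A reader might infer that the protocol expects spontaneous menses after most anovulatory cycles; 7.3 says only that it may occur. Without a window, though, timing cannot do this work.

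**The replacement is still a laboratory value.** It is anchored to 6–8 days after the LH surge, and 7.3 gives a genuine reason for it: a visit moved up by an early false-positive test. This stands, but the anchor is absent when no surge was recorded. Scheduled repeats follow only values below 3, so the scheduled opportunity runs from no to yes. That alone does not favour an arm, since both follow the same repeat rule.

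**Stronger readings.** A reader might infer that the trial is biased towards the combination. Bias needs unequal missingness or unequal replacement, which the documents neither show nor exclude. The 22–41% figure is an extreme assumed case: over three cycles, 1 − 0.85³ = 39% of women in one arm would have at least one missed test, against 1 − 0.95³ = 14% in the other, every one called ovulatory. Nor can one say that both versions in 12.4 always fail under unequal loss; step 5 shows a pattern in which assume-no does not inflate the error.

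**Conclusion.** The concern holds as a defect of prespecification. The stated rules allow menses to create a primary ovulation call, or arguably to displace a recorded progesterone. They leave three treatments of a missing outcome with none primary, and they permit symptom-based replacement without masking.

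The size and direction of the effect cannot be determined from the documents. At the assumed 60% v 80%, the rules span power of 67.5% to 85% at 10% missingness, depending on the rule and the loss pattern. Equal missingness costs power without creating false positives. Unequal missingness can inflate type I error under either version, by an amount that depends on the pattern. This should be fixed because it concerns the primary endpoint and the correction is cheap.

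**What to change.** Change the analysis classification only; dosing and visit management stay as they are.

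- **Sections 3.1.1 and 7.6.** In the primary analysis, count a cycle as ovulatory on a qualifying progesterone or, where the test was missed, on a pregnancy from that cycle confirmed by serum hCG. Without the pregnancy clause, a woman who missed the test and conceived would count as not ovulated. State that menses never overrides a recorded progesterone and that menses-based calls, with a stated window, are a sensitivity analysis only.
- **Section 12.4.** Make the conservative version primary, consistent with the rule above, and report the liberal version beside it. Delete or specify imputation. Tabulate missing tests by arm and cycle, and note that neither version is guaranteed to protect against unequal missingness.
- **Section 3.1.1, replacement.** Remove patient symptoms as a ground. Replace a first value only by a prespecified rule on recorded LH-test, draw and cycle dates, applied without knowledge of arm or result. The rule should cover early false-positive LH tests and cycles with no recorded surge. Report the first-test result alongside, and reconcile the 6–8 day window of 3.1.1 with the 7–9 days in the opening of 7.3.

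**Cost.** Wording in three sections and no new data: LH surge and menses are already logged (4.2, 7.2), serum hCG is already taken (7.4), and event timing is already checked in REDCap (section 11). LH dates remain patient-reported, so discretion is reduced but not removed. A few truly ovulatory missed cycles will not count. At 60% v 80%, power under the conservative rule is 82–85% with 10% of tests missed per cycle. It falls to about 72%, against 80% under the liberal rule, only if all of a 10% dropout leave before any observed ovulation.
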